### 2. Objectives (include all primary and secondary objectives)

- Primary: To determine if the immediate administration of dexamethasone to the post-ablation site diminishes the incidence of post-ablation neuropathic pain
- Secondary: Stratify cervical vs. thoracic vs. lumbosacral data points to compare if post-ablation neuritis is dictated by anatomical location. Also look at the gauge of the needle used in each patient and radiofrequency parameters to see if associated with neuritis incidence. We will track level of disability and effectiveness of ablations with completion of Oswetry Disability Index and/or Neck Disability Index at baseline, 4 weeks, and 8 weeks after completion of bilateral ablations.

**3. Background** (briefly describe pre-clinical and clinical data, current experience with procedures, drug or device, and any other relevant information to justify the research)

Chronic neck and back pain has become one of the leading causes of disability and loss of productivity. This is often associated with poor quality of life, depression, anxiety, and sleep disorders. Conservative measures, such as physical therapy and medications are first-line treatment options and provide improvement of pain in some patients. However, for those who are not responsive to conservative management, interventional procedures are another treatment option. For many patients with facet- or sacroiliac joint-mediated pain who have responded to diagnostic nerve blocks, radiofrequency ablation of the nerve innervating the joints can provide long-term relief. Radiofrequency ablation (RFA) is a relatively safe procedure with minimal risk of adverse events.[1] However, with any procedure involving damage to the peripheral nervous system, there is risk of post-procedure neuropathic pain. Following both lumbar facet joint RFA, and sacroiliac joint RFA, PAN has been documented at a rate ranging from 0.5% to 9.2% per lesion. [2]

PAN is described as a burning pain at the level of the ablation. In patients who have undergone lumbar facet or sacroiliac joint radiofrequency denervation, these symptoms can last anywhere from 2 to 6 weeks. [2,3] Unfortunately, the incidence of PAN is higher in patients who have undergone cervical facet radiofrequency innervation. The incidence is reported to be approximately 19 percent, with an average duration of 2.6 months [4] and can drastically affect a patient's quality of life during this time period.

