### **Study Procedures**

a. Study design, including the sequence and timing of study procedures (distinguish research procedures from those that are part of routine care).

This is a multi-centered double-blinded prospective clinical trial. Patients will be recruited from the pool of patients seen by [name] in the pain management clinic through the Department of Physical Medicine and Rehabilitation. Patients will be recruited from the pools of patients seen by PIs at our collaborating sites (Cornell/Columbia) in the pain management clinic through the Department of Physical Medicine and Rehabilitation. Candidacy for bilateral ablation will be determined by the standard of care, mainly pain relief >50% after two prior bilateral diagnostic blocks. In routine care, these patients are seen in clinic to discuss the risks and benefits of radiofrequency ablation in a clinic. Once patients are consented, they are brought in for the procedure in 2 to 4 weeks. Patients who were not consented in the clinic will also have the opportunity to enroll in the study on the day of their

procedure. They first receive a unilateral lesion, and are brought back to receive a lesion on the other side in no sooner than one week. Patients will then be followed in the clinic in 4 weeks after the procedure to monitor response. Patients can request an earlier appointment if complications arise. If patients develop PAN, they are either monitored without intervention, or initiated on gabapentin or oral corticosteroids, depending on the severity of their symptoms.

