- There will be an initial 2 week follow up asking exclusively about development of post-ablation neuropathic pain. At the two post-procedure visits spaced 4 weeks apart, patients will be given a questionnaire that will ask about development of neuritis, and any adverse reactions after the procedure. If neuritis is present, the onset and duration will also be recorded. If neuritis is present, but the level is generalized or unclear, post-ablation neuritis will be recorded at a single level that most closely matches the clinical presentation. The questionnaire will then be scanned into the patient chart, and reviewed by co-investigators when data collection occurs. Repeat ODI and/or NDI will be filled out at these follow ups to track efficacy of ablations. If patients cannot be seen in clinic at the 4 week or 8 week follow up, co-researchers will follow up with patients by phone.

- c. Study duration and number of study visits required of research participants.

- Patients will be enrolled in the study for approximately 3 months, and will be seen at a total of 4 visits - 1 pre-ablation visit 1 month prior to the procedure, for the procedure itself, and post-ablation for 2 visits spaced 4 weeks apart. There is also a 2 week telephone follow up exclusively assessing incidence of PAN. The study itself will take place over a period of 2 years in order to enroll enough patients to have an adequately powered study.
- d. Blinding, including justification for blinding or not blinding the trial, if applicable.
  - This trial will be double blinded to ensure that there is no bias on the part of the provider performing the procedure or seeing the patient in follow up, or on the part of the patient when reporting outcomes
  - Patient is seen in clinic by either the nurse practitioner, fellow, resident, or [name] (the same applies to collaborating sites and respective PIs) and is identified as needing bilateral ablations of the cervical, thoracic, or lumbar facets, or sacroiliac joints, and is consented for the study.
  - As part of routine care, the provider that saw the patient then notifies the secretary of the procedure that is needed. Information will also be included that the patient is eligible for the study. Subsequently, the secretary will call the patient to set up procedure dates. The same process is to be conducted at our collaborating sites.

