  - The procedure schedule will be sent to [name] (or respective collaborating PIs) and the research team members the night before procedure day with the scheduled patients. Patients in the study will be marked on this schedule.
  - The research team adds the eligible patients to a separate list that is sent to an un-blinded co-investigator with directions on which side to inject dexamethasone or normal saline based on randomization
- e. Justification of why participants will not receive routine care or will have current therapy stopped:
  - Not applicable. All patients in this study will continue to receive routine care, through scheduled ablation procedure and continuation of established medication regimen for pain management.
- f. Justification for inclusion of a placebo or non-treatment group.
  - A placebo group is present to compare the current standard of care and the addition of our intervention and to ensure that any changes are the not the result of the experimental paradigm (i.e. active injection post-lesion).
- g. Definition of treatment failure or participant removal criteria.
  - Treatment failure is defined as the presence of post-ablation neuropathic pain in the period up to 2 months after post-ablation steroid administration.
  - Participant removal criteria:
    - at patient request for removal

- development of immediate onset of weakness or sensory changes post-injection. At that point, the patient will not be given further injections, but data will be used to report an adverse event
- lack of post-procedure follow up
- Any additional procedures that include additional steroid administration

h. Description of what happens to participants receiving therapy when study ends or if a participant's participation in the study ends prematurely.

- Patients will continue with routine care when the study ends or if their participation in the study ends prematurely. They will be continued to be followed at the pain clinic, and if determined to need subsequent radiofrequency ablations after the participation in the study, these will be done routinely without administration of post-ablation dexamethasone or normal saline.

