#### **4. Inclusion/Exclusion Criteria**

- Inclusion:
  - patients followed in the pain management clinic in the Department of Physical Medicine and Rehabilitation who are followed by [name] and PIs from collaborating sites.
  - patients with a diagnosis of either cervical, thoracic, or lumbar facet or sacroiliac joint pain who have responded to medial branch blocks and are already scheduled for bilateral radiofrequency ablations
  - age greater than 18 years old
  - English speaking
- Exclusion:
  - not previously scheduled for radiofrequency ablation of the cervical, thoracic, or lumbar facets, or sacroiliac joints
  - Recent systemic or local corticosteroids in the last 3 months
  - on anticoagulation
  - have a pacemaker
  - age less than 18 years old
  - non-English speaking

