## 6. Study Statistics

- a. Primary outcome variable.
  - Presence of post-ablation neuritis at each lesion site
- b. Secondary outcome variables: none
- c. Statistical plan including sample size justification and interim data analysis.
  - A McNemar's Test will be performed to compare the incidence PAN in the placebo and treatment groups
  - As the most important outcome measure is the nominal measure of whether neuropathic pain develops after ablation, we will collect dichotomous data (neuritic vs. no-neuritic pain). We will perform McNemar's Test to test for a difference in proportions across paired samples (each patient providing his/her own control through unilateral injections of steroid and placebo-saline into each side). We will consider a p-value of less than 0.05 as significant.
  - We will collect a total of 732 samples, where each sample is nerve(s) lesioned on one side; i.e. for a patient receiving a two-level ablation bilaterally, the patient will provide a total of two samples (one experimental-steroid, one placebo-saline). Because we will only collect data from patients with bilateral injections, each acting as his/her own control, the total 732 samples will be comprised of 366 participants for each experimental/placebo condition. We plan to enroll 120 patients at Johns Hopkins and 246 from our collaborating sites in order to get total of 366 participants for each experimental/placebo condition.
  - The sample size was derived through a power-analysis calculation using G\*Power Software (ver. 3.1; Heinrich-Heine Universitat). Specifically, an *a priori* test was performed for the McNemar test with a power of 0.8 and significance level of 0.05. Based on available literature (CITE), we determined that baseline incidence of neuropathic pain is 5%, and further determined that a desirable effect size is a minimum of 50% decrease in incidence with steroid injection (overall incidence of 2.5%). With these values, the contingency table showed an odds ratio of 0.487, and the probability of discordant pairs was 0.0725, leading to a total sample size of 732 (actual power 0.82).
- d. Early stopping rules.
  - study will also be terminated if there appears to be greater than expected (>10%) incidence of PAN in the treatment group during interim analyses

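### Does the lack of a stated time window for neuritis on the saline side leave the paired primary comparison open to bias?

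*Combined protocol and SAP*

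**What the plan says.** Section 6a names the primary outcome as "Presence of post-ablation neuritis at each lesion site". It gives no start, end or assessment time, and section 6c compares the two sides of each patient with McNemar's test.

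The one period attached to neuritis is in Study Procedures, item g, next to the removal criteria: "Treatment failure is defined as the presence of post-ablation neuropathic pain in the period up to 2 months after post-ablation steroid administration". There is no matching statement for the saline side.

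On timing, Study Procedures, item a, says patients "are brought back to receive a lesion on the other side in no sooner than one week"; no maximum is given. Section 2 places the disability questionnaires "at baseline, 4 weeks, and 8 weeks after completion of bilateral ablations". Study Procedures, item b, has neuritis asked about at two visits four weeks apart and adds "Repeat ODI and/or NDI will be filled out at these follow ups to track efficacy of ablations", so the neuritis visits and the disability visits appear to be the same. A two-week call about neuritis alone has no stated starting point. Item b also says "If neuritis is present, the onset and duration will also be recorded". Which treatment goes to the first side is randomised, and the other side gets the alternative.

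**The concern.** Taken together, these sections put the last look 8 weeks after the second ablation. The first side has then been followed for 8 weeks plus the gap, the second for 8 weeks only. If the item g window governed the endpoint, it would open with the steroid injection, and the saline side would be judged over a period unrelated to its own ablation.

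McNemar's test draws only on discordant pairs, and few are expected. A late case counted on one side but not the other can create or hide a discordance, and two analysts reading different sections could classify the same patient differently. For example, take a four-week gap with steroid first. Saline-side neuritis on day 40 after its own ablation falls outside a steroid-dated two months (which closes on saline-side day 33) but counts under section 6a.

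**Working it through.** **Inputs.** Gap g of at least 7 days (Study Procedures, item a); last visit 56 days after the second ablation (section 2 read with item b); 2 months taken as 61 days; 366 pairs, with rates of 5% (saline) and 2.5% (steroid) (section 6c). Assumptions not in the documents: 1:1 order, a gap of 28 days as a long case, and exponential onset with mean m of 7, 14 or 28 days, F(t) = 1 − exp(−t/m).

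**The plan's own figure.** Discordant probability = 0.05 × 0.975 + 0.025 × 0.95 = 0.0725, as stated. Expected discordant pairs: 366 × 0.0725 = 26.5. Expected saline-side cases: 366 × 0.05 = 18.3.

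**Reading 1: section 6a as written, both sides counted to the last visit.** First side 56 + g days, second side 56.
- g = 7: 63 v 56 days. g = 28: 84 v 56 days.
- If a share p of patients has saline first, mean follow-up is 56 + pg for saline and 56 + (1 − p)g for steroid, a difference of (2p − 1)g. At p = 0.5 this is 0 for any gap. At p = 0.6 and g = 7 it is 1.4 days.
- With no true effect, 5% on both sides and 366 pairs, a two-sided exact McNemar test wrongly favours steroid 1.6% of the time. Extra capture of up to 50% on first sides, balanced over the conditions, leaves this at 1.6% to 1.8%.

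**Reading 2: the steroid-dated window applied to both sides.** The saline side has 61 − g days (steroid first) or 61 + g (saline first); the steroid side has 61. Saline capture is [F(61 − g) + F(61 + g)]/2 against F(61).

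| g | m | saline | steroid | relative loss |
|---|---|---|---|---|
| 7 | 14 | 0.986 | 0.987 | 0.2% |
| 7 | 28 | 0.883 | 0.887 | 0.4% |
| 28 | 7 | 0.996 | 1.000 | 0.4% |
| 28 | 14 | 0.952 | 0.987 | 3.6% |
| 28 | 28 | 0.825 | 0.887 | 6.9% |

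At g = 7 and m = 7 the loss is about 0.01%.

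The 61 + g days run past the last visit, so they should be cut at 56 + g, and the steroid side at 56 when it is second. For m = 28:
- g = 7: saline [F(54) + F(63)]/2 = 0.8746; steroid [F(61) + F(56)]/2 = 0.8757; loss 0.13%. A true 50% reduction appears as 49.9%.
- g = 28: saline [F(33) + F(84)]/2 = 0.8212; steroid 0.8757; loss 6.2%. A true 50% reduction appears as 46.7%.

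Of 18.3 saline-side cases, 0.13% is 0.02 of a case and 6.2% is 1.1 cases.

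**Reading 3: the two-month cap applied to the steroid side only.** Mean saline follow-up exceeds steroid by 0.15 week at a 1-week gap and 1.65 weeks at a 4-week gap. With m = 28 and g = 7, capture is [F(63) + F(56)]/2 = 0.8796 against 0.8757, a relative excess of 0.4%. At g = 28 it is 0.9074 against 0.8757, or 3.6%.

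**How long is the gap likely to be?** Study Procedures, item c, describes about 3 months of participation with a visit 1 month before the procedure: 91 − 30 − 56 leaves about 5 days. With the 2- to 4-week lead in item a, 91 − 56 − 28 = 7 to 91 − 56 − 14 = 21 days remain. A 28-day gap fits only with a lead of about a week or consent on the procedure day, which item a allows.

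**The case for a change.** The best case for acting is that the wording is open. Item g, read literally, caps only the steroid side, and randomised order cancels the imbalance only if both sides follow one symmetric rule. With about 27 discordant pairs, a few reclassified sides could matter, and cervical neuritis is reported in section 3 to last 2.6 months on average, so late cases are plausible. The remedy would be one sentence, and a window chosen after unblinding would be open to criticism.

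The silence on the window, on the maximum gap and on the starting point of the two-week call all stands. But item g defines treatment failure; it is not cited in section 6 and is not the variable tested. Using it as a cap on one side only would depart from section 6a, and the excess would still be 0.4% at the minimum gap. The day-40 example needs both that unplanned rule and a four-week gap. At a one-week gap with steroid first, the steroid-dated window closes on saline-side day 54 and the last visit is on day 56, so the readings part company over about two days.

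Carry-over is a separate matter. If 25%, 50% or 100% of the steroid effect reached saline sides lesioned second, the saline rate would be 0.05 − 0.0125c, and a true 50% reduction would appear as 47%, 43% or 33%. Those shares are pure assumptions, and zero is equally compatible with the documents. A first-side comparison of 183 v 183 patients at 5% v 2.5% has about 24% power, so a table by order would settle little. Nor is there a contradiction over steroid exposure: "Recent systemic or local corticosteroids in the last 3 months" is an entry criterion, and the removal rule in item g can be read as covering steroid procedures beyond the study injections.

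**Conclusion.** The gap is one that analysts will fill sensibly. Counting each side to the last visit follows section 6a, and with randomised order at 1:1 it gives equal mean follow-up by condition. An analyst who prefers equal periods within the pair can use the onset already recorded. Neither route needs new data.

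At the only gap the plan states, one week, the steroid-dated reading costs 0.4% of saline-side cases at most, or 0.13% once the last visit is respected (mean onset 28 days), well under one case in 366 pairs. The 6.2% figure needs a four-week gap, slow onset and a rule the plan does not adopt, and even then a 50% reduction would appear as 46.7%. The conclusion rests on roughly balanced order, on neuritis visits dated from the second ablation (an inference from sections read together), and on the assumed onset distributions. A written window would be tidier, but the expected gain is negligible, so no change to the plan follows.

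### Immediate sensory change after injection is a ground for removal from the study, yet it can overlap the primary endpoint, so removal can depend on the outcome

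*Combined protocol and SAP*

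**What the plan says.** Study Procedures, section g, covers treatment failure and removal together. Treatment failure is PAN arising within two months of the post-ablation steroid; no lower limit on onset is set. The removal list that follows includes "development of immediate onset of weakness or sensory changes post-injection. At that point, the patient will not be given further injections", and adds that the data will go into an adverse event report. The other grounds on the list are the patient's own request, missing follow-up, and further procedures involving steroid.

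The Background gives the only description of the endpoint: "PAN is described as a burning pain at the level of the ablation". Under Study Procedures, the follow-up questionnaire captures timing ("If neuritis is present, the onset and duration will also be recorded"), but no rule uses that timing to decide what counts. Study Statistics makes the primary outcome the presence of neuritis at each lesion site, compared by McNemar's test within patients who have steroid on one side and saline on the other. It names no analysis population and does not say how removed patients are counted.

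**The concern.** A single bullet does two jobs. It stops further injections, which is clinical management and not questioned here, and it removes the participant, which affects the data. The trigger is a sensory change, and burning neuropathic pain is one. Neither the word immediate nor the term sensory changes is defined, so two sites could handle the same symptom on the same day differently: one records PAN, the other removes the patient.

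This is not simply the problem of incomplete pairs. A patient whose symptom follows the first injection gets no second side and cannot form a pair. A patient whose symptom follows the second injection already has a complete pair, but meets the removal criterion all the same.

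At stake are the scheduled PAN assessments of patients who may be having the event the trial is designed to count. At the planned rates there are few such events: 366 × 0.05 = 18.3 on saline sides and 366 × 0.025 = 9.2 on steroid sides. A handful handled differently would show. The early stopping rule, which depends on PAN incidence in the treatment group, would also miss any event recorded only as an adverse event.

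**Working it through.** **The text.** Take burning pain at the ablated level that begins straight after injection.

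- Against the endpoint: it fits the Background description, falls inside the two-month window, and has no minimum onset to fail.
- Against the removal criterion: it is immediate, follows the injection, and is a sensory change.
- Precedence: neither section says which applies.
- Consequence of removal: section h returns patients who leave early to routine care in the pain clinic. The 2-week PAN call and the questionnaires at the two later visits are listed as steps the study adds, so these are what may be lost.

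**The plan's own figures.** Inputs from Study Statistics: saline rate 5%, steroid rate 2.5%, "power of 0.8 and significance level of 0.05", sidedness not stated. With independent sides:

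- saline-only pairs: 0.05 × 0.975 = 0.04875
- steroid-only pairs: 0.025 × 0.95 = 0.02375
- sum 0.0725; ratio 0.02375 / 0.04875 = 0.487

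These match the plan: "the contingency table showed an odds ratio of 0.487, and the probability of discordant pairs was 0.0725". With 732 × 0.0725 ≈ 53 discordant pairs, a one-sided exact test rejects at 33 or more of 53 (actual alpha 0.0492) with power 0.822, against the stated 0.82. So 732 reproduces as pairs with a one-sided test, whereas the plan provides 366 pairs. That is a separate matter, but it explains why the baseline power below is low.

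**Equal removal on both sides.** Let f be the share of PAN classed as immediate sensory change. The documents do not give f; it is an assumption. Suppose the whole pair is lost.

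- Proportion kept: k = (1 − 0.05f)(1 − 0.025f)
- Patients removed: 366(1 − k). For f = 0.30: k = 0.985 × 0.9925 = 0.9776, so 366 × 0.0224 = 8.2
- Discordant probability among those kept: 0.0725(1 − f)/k

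| f | Removed of 366 | P(discordant) | Odds ratio | Exact two-sided power |
|---|---|---|---|---|
| 0 | 0 | 0.0725 | 0.487 | 0.35 |
| 5% | 1.4 | 0.069 | 0.487 | 0.33 |
| 10% | 2.7 | 0.066 | 0.487 | 0.31 |
| 20% | 5.5 | 0.059 | 0.487 | 0.28 |
| 30% | 8.2 | 0.052 | 0.487 | 0.24 |

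The factor (1 − f)/k cancels from the odds ratio, so equal removal costs power without biasing that ratio.

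**Unequal removal.** True risk ratio 0.50.

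- 20% of events removed on saline sides only: 0.05 × 0.8 / 0.99 = 0.0404; 0.025 / 0.0404 = 0.62
- 20% on steroid sides only: 0.025 × 0.8 / 0.995 = 0.0201; 0.0201 / 0.05 = 0.40
- 30% saline, 10% steroid: 0.035 v 0.0225, an apparent reduction of 1 − 0.0225/0.035 = 36%
- 10% saline, 30% steroid: 0.045 v 0.0175, an apparent reduction of 1 − 0.0175/0.045 = 61%

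The last two lines keep all patients in the denominator; taking the removed patients out moves them by less than one percentage point.

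**The case against.** The strongest reply is that the bullet is a safety rule for acute neurological complications. It pairs sensory change with weakness, ties both to the injection, and does not mention pain, while the same section uses a different term for the endpoint. The plan treats PAN as an inflammatory event lasting weeks and first asks about it at two weeks. The immediate share could be close to zero. This limits the point to immediate onset; it does not remove the overlap, because nothing in the plan excludes immediate burning pain from either category.

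A reader might go further and infer any of the following, none of which the documents support:

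- *That early PAN in general is taken out of the primary outcome.* PAN starting over the following days, or first reported at the 2-week contact, is not immediate and is not covered.
- *That removed patients survive only as adverse event reports and are dropped from the McNemar table.* The plan states one use of the data but does not say it is the only one, and it is silent on the analysis population. Exclusion is an inference.
- *That the rule hides benefit.* That would need proportionately more removals on saline sides, for which no passage gives evidence; the opposite pattern exaggerates the benefit.
- *That these patients go unobserved.* Section h keeps them under pain-clinic follow-up.
- *That all burning pain should count as PAN whatever its onset.* The Risks section lists injection-site pain (0.5%) separately from neuritis, so that case definition is a clinical judgement for the investigators.

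**Conclusion.** The point holds in a limited form. Following section g as written removes participants after randomisation for an event that can overlap the endpoint, and can end their scheduled PAN assessments even when both sides have been injected. This goes beyond a missing definition, because removal is a stated rule.

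The size is unknown. On the plan's 5% and 2.5% rates, independent sides and an assumed immediate share of 5% to 30%, about 1 to 8 of 366 patients are affected. If their pairs are also left out of the analysis, two-sided exact power falls by 0.02 to 0.11 from 0.35; the low starting value has a different cause and should not be charged to this rule. The direction of any bias cannot be predicted. The change is worth making because it is cheap, not because a large effect has been shown.

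**What to change.** Leave the no-further-injection instruction unchanged, and separate stopping injections from removal from the study. State that patients meeting this criterion:

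- stay in the scheduled 2-, 4- and 8-week PAN and adverse-event contacts;
- remain in the McNemar analysis if both sides were injected, with PAN assessed exactly as for everyone else;
- are reported in PAN incidence by injectate if only one side was injected. The protocol should say from which date their contacts run, since the disability-index schedule is dated from completion of both sides.

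The investigators should reconcile the removal criterion with the PAN definition so that one symptom is not handled both ways; how they draw that line is a clinical matter. The cost is protocol wording, a few additional follow-up contacts, and possibly slightly higher reported PAN rates.

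### Does the plan need a rule for patients removed after both sides are treated, and an enrolment allowance for losing them?

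*Combined protocol and SAP*

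**What the plan says.** Study Procedures, item g, gives four grounds for removal: the patient's request, immediate weakness or sensory change after injection, "lack of post-procedure follow up", and "Any additional procedures that include additional steroid administration". Only the weakness ground says what happens to the data, and it mentions only adverse-event reporting. The same item states: "Treatment failure is defined as the presence of post-ablation neuropathic pain in the period up to 2 months", counted from steroid administration. Item h adds, for patients whose participation ends early: "They will be continued to be followed at the pain clinic".

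On outcome collection, Study Procedures, item b, says: "There will be an initial 2 week follow up asking exclusively about development of post-ablation neuropathic pain". Two visits 4 weeks apart follow, and if a patient cannot attend, "co-researchers will follow up with patients by phone".

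Section 6, item c, compares paired sides by McNemar's test at 0.05 and restricts data to patients injected on both sides. On numbers it says: "We plan to enroll 120 patients at Johns Hopkins and 246 from our collaborating sites", which makes 366. Section 6, item d, ends the study if there appears to be "greater than expected (>10%) incidence of PAN in the treatment group during interim analyses". Neither item defines an analysis set, a rule for missing outcomes, or a denominator for the 10% figure.

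**The concern.** A patient can have both sides treated, report PAN at 2 weeks, and then meet a removal criterion before 8 weeks. The restriction to bilateral patients settles the case of someone who never receives the second side, but not this one. If the patient is dropped, a pair is lost from a test expected to rest on about 26.5 discordant pairs. A PAN event may also leave the numerator of the stopping rule. Because the choice is not written down, it could in principle be made after the data are seen. Since enrolment equals planned pairs, every dropped patient also leaves the trial below its own target. At stake would be the timing of a rule that can end the study, and some of the primary test's power.

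**Working it through.** **Inputs.** From section 6, item c: PAN 5% with saline and 2.5% with steroid, discordant proportion 0.0725, odds ratio 0.487, 366 patients. From section 6, item d: the 10% limit. The interim size of 183 (half of 366), the removal shares and the loss rates are assumptions; the documents give none of them.

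**1. The plan's own figures.** Taking the two sides as independent:
- Saline-only PAN: 0.05 × 0.975 = 0.04875.
- Steroid-only PAN: 0.025 × 0.95 = 0.02375.
- Sum 0.0725 and ratio 0.02375/0.04875 = 0.487, both as stated.
- Expected discordant pairs: 366 × 0.0725 = 26.5.
- PAN on either side: 0.0725 + 0.05 × 0.025 = 0.07375.

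**2. Removal related to PAN but not to which side had steroid.** If a share r of patients with any PAN is dropped, both discordant cells shrink by (1 − r). The odds ratio is 0.02375(1 − r)/0.04875(1 − r) = 0.487 for every r. The discordant count is 26.535(1 − r), and the difference in incidence is 0.025(1 − r)/(1 − 0.07375r).

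| r | Discordant pairs | Difference (points) |
|---|---|---|
| 0 | 26.5 | 2.5 |
| 0.1 | 23.9 | 2.3 |
| 0.2 | 21.2 | 2.0 |
| 0.3 | 18.6 | 1.8 |

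**3. Removal unrelated to PAN.** Two-sided McNemar power at 0.05, averaged over the binomial number of discordant pairs:

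| Loss | Pairs left | Exact | Chi-square, uncorrected |
|---|---|---|---|
| 0 | 366 | 0.350 | 0.442 |
| 5% | 348 | 0.332 | 0.425 |
| 10% | 329 | 0.314 | 0.406 |
| 20% | 293 | 0.279 | 0.367 |

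The top row is low before anyone is lost, because the stated 732 reproduces as a number of pairs. An exact one-sided test first reaches 0.80 power at 53 discordant pairs (0.8215, the stated 0.82), and 53/0.0725 rounds up to 732. That is a separate matter. Dividing 366 by (1 − loss) gives 386, 407 or 458 patients for 5%, 10% or 20% loss, and only preserves the 0.350.

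**4. The 10% rule.** At 183 patients the limit is first exceeded at 19 events.
- One patient with steroid-side PAN dropped: 19/183 = 10.4% becomes 18/182 = 9.9%. The rule no longer triggers.
- Four patients without steroid-side PAN dropped: 18/183 = 9.8% becomes 18/179 = 10.06%. The rule now triggers.
- The binomial chance of 19 or more events in 183 is about 2 in 10 million at the planned 2.5%, and about 0.2% even at 5%.

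The handling of a few removals therefore matters only if the true steroid-side rate is already close to 10%, four times the planned rate. If only patients with PAN were dropped, with saline PAN at 5%, the true rate needed to reach 10% would be (0.1 − 0.005r)/(1 − 0.905r) = 10.9%, 12.1% or 13.5% for r = 0.1, 0.2 or 0.3. That needs a one-way link between PAN and removal.

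**5. Is there such a link in the text?** The steroid ground concerns procedures. Study Procedures, item a, manages PAN by monitoring, gabapentin or oral corticosteroids, none of which is a procedure on a plain reading. The weakness ground withholds further injections, which mainly fits removal before the second side. What mainly remains is patient request, missed follow-up (softened by telephone contact) and steroid procedures for other reasons. Nothing in item g says recorded outcomes are discarded.

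**The case for a change.** The strongest opposing case is that a rule able to end a study should not have an undefined denominator, and that a few sentences in section 6 would settle it at little cost. No other passage closes the gap. The treatment-failure definition is worded for steroid administration only, so it cannot define the saline half of a pair. Item h promises routine care, not recording of study outcomes. Telephone follow-up limits losses but is not an analysis rule.

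All of that stands as a description of the text. What does not stand is the step from an unwritten rule to a wrong result. The harm to the stopping rule needs an assumed interim size, assumed removal shares and an assumed direction, and step 4 shows the direction can reverse. Blinding of patients and of the treating and follow-up clinicians also makes it unlikely that removal depends on which side received steroid, the condition under which the odds ratio would be biased.

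Nor does a written rule resolve everything. Counting PAN recorded on one side before removal conflicts with admitting only pairs known on both sides when the other side is missing. A person lost to follow-up usually loses both sides together. Setting both to PAN, or both to no PAN, then creates concordant pairs, which McNemar's test ignores.

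**Conclusion.** No change follows. Section 6 omits a detail that the paired design largely supplies: use every patient with both sides treated and PAN status known for both, count PAN recorded before removal, and report removals by reason. Following the plan as written is not shown to give a wrong answer. The odds ratio stays at 0.487 provided removal does not depend on which side had steroid. The cost to power is modest: 0.350 to 0.314 at an assumed 10% loss, and to 0.279 at 20%. The 10% rule is sensitive only near a true rate of 10%, and then in either direction. The missing loss allowance adds nothing on its own, since it would inflate a 366-pair target whose adequacy is a separate question. The conclusion would weaken if PAN itself commonly led to removal, for example if oral corticosteroids given for PAN were treated as a removal ground; the documents do not say so.
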